3.4 Additional Endpoints

Study 1 (bDMARD-IR AS):

Additional endpoints are the following measurements assessed at scheduled time points other than those specified for the primary and secondary endpoints:

Binary variables:

- ASAS20 response;
- ASAS40 response;
- BASDAI 50 response;
- ASAS PR;
- ASDAS ID (ASDAS score < 1.3);
- ASDAS LDA (ASDAS score < 2.1);
- ASDAS Major Improvement (a change from Baseline of ≤ -2.0);
- ASDAS Clinically Important Improvement (a change from Baseline of ≤ -1.1);
- Discontinuation of opioids among subjects with opioid use at Baseline.

Change from Baseline in:

- ASAS HI;
- ASDAS;
- ASQoL;
- BASDAI and BASDAI components including mean of question 5 and 6 of the BASDAI;
- BASFI;
- BASMI_{lin};
- High sensitivity C-reactive protein (hsCRP);
- EuroQoL-5D-5L (EQ-5D-5L);
- Functional Assessment of Chronic Illness Therapy-Fatigue (FACIT-F);
- MASES;
- Modified Stoke Ankylosing Spondylitis Spine Score (mSASSS) with conventional radiograph;
- MRI SPARCC score of SI joints;
- MRI SPARCC score of spine;

- Patient's Assessment of Total Back Pain (Total Back Pain);
- Patient's Assessment of Nocturnal Back Pain (Nocturnal Back Pain);
- Patient's Global Assessment of Pain;
- Physician's Global Assessment of Disease Activity (PGA);
- Patient's Global Assessment of Disease Activity (PtGA);
- 36-Item Short Form Health Survey (SF-36);
- Tender joint count (TJC) and swollen joint count (SJC);
- Work Productivity and Activity Impairment (WPAI);
- NSAID score;
- Physical Activity Assessment (step count, physical activity, and spinal range of motion tasks) as measured by a wearable device (except in countries where the digital health technology device is not available or is not allowed to be used in the study by the local regulatory authority).

Additional endpoint relating to the assessment of disease flare for subjects on upadacitinib treatment who achieve an ASDAS C-reactive protein (CRP) < 1.3 at Week 52 and an ASDAS (CRP) < 2.1 at Week 40:

- Time to flare during Week 52 to Week 104

Study 2 (nr-axSpA):

Additional endpoints are the following measurements assessed at scheduled time points other than those specified for the primary and secondary endpoints:

Binary variables:

- ASAS20 response;
- ASAS40 response;
- BASDAI 50 response;
- ASAS PR;
- ASDAS ID (ASDAS score < 1.3);
- ASDAS LDA (ASDAS score < 2.1);
- ASDAS Major Improvement (a change from Baseline of ≤ -2.0);
- ASDAS Clinically Important Improvement (a change from Baseline of ≤ -1.1);
- Discontinuation of opioids among subjects with opioid use at Baseline.

Change from Baseline in:

- ASAS HI;
- ASDAS;

- ASQoL;
- BASDAI and BASDAI components including mean of question 5 and 6 of the BASDAI;
- BASFI;
- BASMI_{lin};
- hsCRP;
- EQ-5D-5L;
- FACIT-F;
- MASES;
- mSASSS with conventional radiograph;
- MRI SPARCC score of SI joints;
- MRI SPARCC score of spine;
- Total Back Pain;
- Nocturnal Back Pain;
- Patient's Global Assessment of Pain;
- PGA;
- PtGA;
- SF-36;
- TJC and SJC;
- WPAI;
- NSAID score.

Additional endpoint relating to the assessment of disease flare for subjects in the upadacitinib group who achieved an ASDAS (CRP) < 1.3 at Week 52 and an ASDAS (CRP) < 2.1 at Week 40:

- Time to flare during Week 52 to Week 104

Study 1 and Study 2: Remission-Withdrawal Period

Additional endpoint relating to the assessment of disease flare:

- Time to flare during the withdrawal period

Additional endpoints assessed at scheduled visits during the withdrawal period:

Binary variables:

- ASDAS (CRP) ID/LDA
- ASDAS (CRP) Major Improvement/Clinically Important Improvement

- ASAS 40/20/PR
- BASDAI 50

Change from baseline (of Double-Blind Period) in:

- ASDAS (CRP) (and components)
- BASDAI (and components)
- Total back pain
- BASFI
- PtGA
- Patient's Global Assessment of Pain
- Nocturnal back pain
- ASAS HI
- TJC/SJC
- BASMI_{lin}
- MASES
- PGA

Additional endpoints assessed at scheduled visits during re-treatment of upadacitinib after disease flare:

Binary variables:

- ASDAS (CRP) ID/LDA
- ASDAS (CRP) Major Improvement/Clinically Important Improvement
- ASAS 40/20/PR
- BASDAI 50

Change from re-treatment baseline (i.e., at the time of flare) in:

- ASDAS (CRP) (and components)
- BASDAI (and components)
- Total back pain
- BASFI
- PtGA
- Patient's Global Assessment of Pain
- Nocturnal back pain
- ASAS HI

- TJC/SJC
- BASMI_{lin}
- MASES
- PGA

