Long-term efficacy analysis will be performed similarly as described above, corresponding to the composite estimand for binary endpoints and the treatment policy estimand for continuous endpoints. For binary endpoints, supplementary analysis using the treatment policy estimand may also be conducted on all data as observed. For efficacy analysis beyond the placebo-controlled period (Week 14 in Study 1 [bDMARD-IR] and Week 52 in Study 2 [nr-axSpA]), no statistical comparison will be performed; descriptive statistics and 95% CIs will be provided. The analyses will be performed by randomized treatment sequence as described below:

1. Placebo → upadacitinib 15 mg QD
2. Upadacitinib 15 mg QD → upadacitinib 15 mg QD

Efficacy Analysis for the Remission-Withdrawal Period

For time to flare during the withdrawal period, the Kaplan-Meier (KM) curve will be provided based on as observed data. Subjects who discontinue the Remission-Withdrawal Period (prior to observed flare) will be considered censored. Subjects who receive retreatment will be considered flared. The KM estimator and associated 95% CIs for the flare-free rate during the withdrawal period will be provided. Similar analyses will also be performed for time to flare between Week 52 and Week 104 for Study 1 and Study 2 as well as for M16-098 (SELECT-AXIS 1).

For analysis of binary endpoints at scheduled visits during the withdrawal period, non-responder imputation will be used, where subjects who flare, discontinue the study, or have missing values are considered non-responders. For analysis of continuous endpoints, MMRM will be used. For all endpoints, analysis based on as observed data will also be performed. Descriptive statistics and 95% CIs will be provided. Data after retreatment will be excluded from these analyses and analyzed separately.

For subjects who receive re-treatment of upadacitinib after disease flare, analysis of endpoints after re-treatment will be based on data as observed. Change from baseline and improvement response are calculated from the retreatment baseline. Descriptive statistics and 95% CIs will be provided.

Subgroup Analysis for Efficacy

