2.2 Study Design Overview

Figure 1 shows the design of Study M19-944. Remission-Withdrawal Period is illustrated in the right portion.

Figure 1. Study Schematic

AS ankylosing spondylitis; ASAS Assessment of Spondyloarthritis International Society; bDMARD IR biologic disease modifying antirheumatic drug inadequate responder; EMA European Medicines Agency; FDA Food and Drug Administration; MRI magnetic resonance imaging; nr axSpA non radiographic axial spondyloarthritis; QD once daily; SI sacroiliac; UPA upadacitinib

Subjects in Study M19-944 from both Study 1 (AS bDMARD-IR) and Study 2 (nr-axSpA) who reach Week 104 on study drug (upadacitinib 15 mg QD) will be assessed whether they are in remission, with an ASDAS (CRP) < 1.3 at Week 104 and an ASDAS (CRP) < 2.1 at Week 88.

Subjects in remission at Week 104 will be eligible for the Remission-Withdrawal Period. Subjects will be followed without study drug treatment and assessed for disease flare through Week 152. Flare is defined as an ASDAS (CRP) \geq 2.1 at 2 consecutive visits (based on observed records), which are at least 2 weeks apart, or an ASDAS (CRP) > 3.5 at one visit. Subjects who flare will receive open-label re-treatment upadacitinib

15 mg QD from the time of flare for 24 weeks (re-treatment) or longer per local country requirements. Subjects who do not flare will be followed without upadacitinib treatment until Week 152 at which point they will have the option to receive open label upadacitinib for the predefined time period, if Week 152 is before the end of the Open-Label Extension Period for their respective country. If Week 152 is after the end of the Open-Label Extension Period, the subject will complete the study at Week 152.

Efficacy analyses will be performed to characterize subject response to treatment withdrawal up to 48 weeks and response to upadacitinib re-treatment for 24 weeks respectively. Safety analyses will be performed to assess safety of reinitiated upadacitinib 15 mg QD after treatment withdrawal, including re-treatment after flare and treatment during Open-Label Extension Period after withdrawal.

An additional safety analysis will be performed to assess the totality of upadacitinib safety in the M19-944 study.

For the purposes of subject disposition and efficacy analysis, the duration of withdrawal from treatment is defined as the Withdrawal Period. The 24 weeks of exposure to treatment after flare is defined as the Re-treatment Period.

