For the purposes of baseline characteristics, efficacy analysis and safety analysis, Original Baseline is defined as the value last observed prior to the first administration of study drug in the parent study, Study 1 or Study 2. The Original Baseline is used as the baseline value for all change or percent change from baseline efficacy analyses in the Withdrawal Period and for all safety summaries. For the purposes of efficacy analysis, Re-treatment Baseline is defined as the baseline value of the Re-treatment Period, which is the value last observed prior to the first administration of re-treatment study drug in the Remission-Withdrawal Period. The Re-treatment Baseline is used as the baseline value for all change or percent change from baseline efficacy analyses in the Re-treatment Period.

All analyses and summary will be performed and presented for overall (all eligible subjects) and by indication for Study 1 (bDMARD-IR AS) and Study 2 (nr-axSpA) subgroups (eligible subjects enrolled in Study 1 and Study 2, respectively).

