4.0 Analysis Populations

The Analysis Populations are defined in [Table 1](#) and [Table 2](#) below.

[figure not shown]
Table 1. Analysis Population for Efficacy Analyses

Analyses Population	Definition	Analyses Group
Withdrawal Analysis Set (WAS)	All subjects who entered the Remission-Withdrawal Period	Off Upadacitinib Treatment
Re-treatment Analysis Set (RAS)	All subjects who entered the Remission-Withdrawal Period and received at least one dose of Upadacitinib re-treatment in the Remission-Withdrawal Period	Upadacitinib 15 mg Re-treatment in RW

Table 2. Analysis Population for Safety Analyses

[figure not shown]
Analyses Population	Definition	Analyses Group	Data for Analyses
UPA reinitiation	All subjects who received at least one dose of reinitiated upadacitinib	Upadacitinib 15 mg	Safety data after reinitiation of upadacitinib (i.e., F+G+H as shown in Figure 2) will be included in safety analyses for summary of safety after reinitiating upadacitinib.
ALL UPA	All subjects who received at least one dose of upadacitinib in M19-944.	Any Upadacitinib 15 mg	Safety data under upadacitinib exposure in M19-944 (i.e., A+C+E+F+G+H in Figure 3) will be included in safety analyses for the totality of upadacitinib safety in M19-944.

Figure 2. Study Drug Exposure for Reinitiated Upadacitinib (UPA reinitiation)

Study 1 includes 14 week double blind placebo controlled period with 90 week open label period. Study 2 includes 52 week double blind placebo controlled period with 52 week open label period.

Figure 3. Study Drug Exposure for All Upadacitinib (ALL UPA)

Study 1 includes 14 week double blind placebo controlled period with 90 week open label period. Study 2 includes 52 week double blind placebo controlled period with 52 week open label period.

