8.0 Handling of Potential Intercurrent Events

For the Withdrawal Period, the potential intercurrent event is upadacitinib re-treatment. The following strategies will be used to handle the intercurrent event in efficacy analysis:

- For time-to-flare endpoint, the composite strategy will be used. Subjects who receive upadacitinib re-treatment without meeting disease flare criterion will be considered flared at the time of first dose.
- For binary endpoints, the composite strategy will be used to handle intercurrent events. Subjects who receive upadacitinib re-treatment will be considered as non-responder for all Withdrawal Period visits after first dose date.
- For continuous endpoints, the hypothetical strategy will be used to handle intercurrent events. All data after first dose date of upadacitinib re-treatment will be excluded from analysis and will be implicitly imputed by the statistical model.

For the Re-treatment Period, the potential intercurrent event is premature discontinuation of re-treatment study drug. The following strategy will be used to handle the intercurrent event in efficacy analysis:

- For all endpoints, the treatment-policy strategy will be used to handle intercurrent events. All collected efficacy data will be used as observed, regardless of whether the subject discontinued re-treatment study drug prior to the completion of the Re-treatment Period.

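### The re-treatment endpoints describe response after flare, but the SAP's Re-treatment Analysis Set requires only one re-treatment dose and so could include subjects who never met the flare criterion

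*Protocol*

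**What the plan says.** The protocol ties the re-treatment question to flare in three places. Section 3.4 introduces the outcomes as "Additional endpoints assessed at scheduled visits during re-treatment of upadacitinib after disease flare" and sets the reference point for the continuous ones: "Change from re-treatment baseline (i.e., at the time of flare) in". Section 7.3 states the analysis: "For subjects who receive re-treatment of upadacitinib after disease flare, analysis of endpoints after re-treatment will be based on data as observed".

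SAP section 2.2 uses the same idea for the time window: "The 24 weeks of exposure to treatment after flare is defined as the Re-treatment Period".

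The SAP's analysis set and baseline do not carry the condition. Table 1 in section 4.0 defines the RAS as "All subjects who entered the Remission-Withdrawal Period and received at least one dose of Upadacitinib re-treatment in the Remission-Withdrawal Period". Re-treatment Baseline in section 2.2 is the value "which is the value last observed prior to the first administration of re-treatment study drug in the Remission-Withdrawal Period", with no link to flare.

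SAP section 8.0 provides for the subjects in question: "Subjects who receive upadacitinib re-treatment without meeting disease flare criterion will be considered flared at the time of first dose". That rule is listed under the Withdrawal Period, for the time-to-flare endpoint. For the Re-treatment Period, section 8.0 names one intercurrent event only, stopping the re-treatment drug early, and applies a treatment-policy strategy. Sections 9.3.1 and 9.3.2 analyse observed data, with no imputation for binary endpoints and no flare-confirmed subset.

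**The concern.** The re-treatment tables will be read as the chance of regaining disease control once it has been lost. That reading needs every subject in the denominator to have lost control first. As Table 1 is worded, a subject given re-treatment without meeting the flare criterion enters the denominator, and the SAP expects that this may happen.

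LDA and Inactive Disease are absolute thresholds on ASDAS (CRP), below 2.1 and below 1.3. A subject who starts re-treatment below 2.1 has not lost LDA at that point, and can be counted as an LDA responder at later visits without having regained anything. The same subject has little room to fall further, and so pulls down the endpoints measured as improvement from Re-treatment Baseline. There is no formal test in this period, so the estimates are the result and their denominator should match the question.

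**Working it through.** **Plan's own figure.** There is none to reproduce. The documents give no expected number of re-treated subjects, no expected number re-treated without flare, and no expected LDA rate for this period.

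**Step 1: why baseline status matters.** Flare needs ASDAS (CRP) at or above 2.1 at two consecutive visits at least 2 weeks apart, or above 3.5 at one visit (protocol section 4.1, SAP section 2.2). SAP section 3.1 has above 2.1 for the two-visit arm. LDA is below 2.1 (SAP section 3.2). On either wording, a subject who meets the criterion is out of LDA at the qualifying visits. A subject who has not met it may be either:
- below 2.1, and so already in LDA at Re-treatment Baseline; or
- at a single unconfirmed value of 2.1 to 3.5, and so neither flared nor in LDA.

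**Step 2: effect on a response rate.** Let f be the share of the RAS re-treated without meeting the criterion, p the response rate in flared subjects and q the rate in the others.

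RAS rate − flare-only rate = (1 − f)p + fq − p = f(q − p)

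All three inputs are assumptions. LDA results, in percentage points:

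| Assumed p, q | f = 0 | f = 5% | f = 10% | f = 20% |
|---|---|---|---|---|
| 0.75, 0.95 | 0 | 1.0 | 2.0 | 4.0 |
| 0.60, 0.95 | 0 | 1.75 | 3.5 | 7.0 |
| 0.50, 1.00 | 0 | 2.5 | 5.0 | 10.0 |
| 0.70, 0.70 | 0 | 0 | 0 | 0 |
| 0.70, 0.40 | 0 | −1.5 | −3.0 | −6.0 |

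For example, 0.20 × (0.95 − 0.60) = 0.07. The last row is the case where most non-flared subjects start outside LDA and do worse than flared subjects.

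**Step 3: improvement endpoints.** Protocol section 3.4 defines Major Improvement as an ASDAS change of −2.0 or lower and Clinically Important Improvement as −1.1 or lower. From a baseline below 2.1:
- Major Improvement needs a final ASDAS below 2.1 − 2.0 = 0.1.
- Clinically Important Improvement needs a final ASDAS below 2.1 − 1.1 = 1.0.

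Take the limiting assumption that such subjects never reach these (q = 0), with p = 0.60 and f = 10%. The effect is 0.10 × (0 − 0.60) = −6 points.

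**Step 4: mean change.** Assume a mean ASDAS change of −1.5 in flared and −0.2 in non-flared subjects, a gap of 1.3. The observed mean fall is then diluted by f × 1.3: 0.05 × 1.3 = 0.065 units at 5% and 0.20 × 1.3 = 0.26 units at 20%. It is 0 if f = 0.

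**The case against.** **Re-treatment is given only on flare.** Protocol section 4.1 and Appendix F, and SAP sections 2.2 and 2.3, offer re-treatment to subjects who flare. Re-treatment without flare would depart from the plan, and the section 8.0 rule is a contingency. This stands, and it means the number affected may be zero. It does not remove the gap, because the SAP wrote a rule for these subjects in one analysis and left the other silent.

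**The analysis window already implies flare.** SAP section 9.3.2 analyses the Re-treatment Period, which section 2.2 defines as following flare. Read together, these could be taken to exclude non-flared subjects. But Table 1 is where the set is defined, and a programmer following it would include them.

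**Re-treated subjects count as flared.** Protocol section 7.3 says "Subjects who receive retreatment will be considered flared", in line with SAP section 8.0. Both statements concern time to flare, where a composite rule is sensible. Neither changes a subject's ASDAS when re-treatment starts.

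**These are additional endpoints, summarised descriptively.** SAP sections 9.1 and 13.0 confirm that there is no testing. Deviations such as wrong treatment are also to be listed under SAP Appendix B, so some cases may be visible. This limits the weight of the point; it does not make the denominator fit the question.

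A reader might also infer that the RAS takes in non-flaring subjects who start open-label drug after Week 152. Its wording does not support this: it is confined to re-treatment within the Remission-Withdrawal Period. Those later starters belong to the UPA reinitiation safety set.

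**Conclusion.** The mismatch is in the text: the endpoint is response after flare, the analysis set is anyone dosed, and the SAP foresees subjects who fall between the two. The consequence is conditional. If such subjects occur and start below 2.1, LDA and Inactive Disease rates could be overstated, and improvement rates and mean change understated. The effect is zero if there are none. For subjects with a single unconfirmed value of 2.1 to 3.5 the direction can reverse.

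The size rests wholly on assumptions. For a share of 0% to 20%, with LDA rates of 95% in non-flared and 60% to 75% in flared subjects, the overstatement is 0 to 7 points. It reaches 10 points at the more extreme pairing of 100% and 50%, and is negative if the non-flared rate is lower.

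Two stronger readings are tempting and should not be drawn. One is that LDA recapture is overstated as a matter of fact; with no count of such subjects and no rates, the documents cannot show this. The other is that a subject below 2.1 at Re-treatment Baseline counts as a responder at every later visit; LDA is judged from the observed ASDAS at each visit, so the subject counts only where the value stays below 2.1.

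**What to change.** 1. Reconcile the flare threshold first. The protocol synopsis, protocol section 4.1 and SAP section 2.2 use at or above 2.1 for the two-visit arm; SAP section 3.1 uses above 2.1. A subject at exactly 2.1 on two visits has flared under one text and is re-treated without meeting the criterion under the other. Until the passages agree, a flare-confirmed subset could drop subjects who were re-treated in line with the protocol. No view is taken here on which threshold should stand.
2. In SAP Table 1 and section 9.3, base the main re-treatment efficacy tables on RAS subjects who met the reconciled criterion before their first re-treatment dose.
3. Report the number re-treated without meeting it, and their LDA status at Re-treatment Baseline.
4. Give the all-dosed RAS as a supportive analysis.
5. Leave the Kaplan-Meier composite rule and both safety populations unchanged.

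The cost is the threshold reconciliation, a short change to Table 1 and section 9.3, one flag variable and one supportive set of tables. The efficacy set may be slightly smaller. A few subjects may count as flared in the Kaplan-Meier analysis yet be absent from the main re-treatment tables; a footnote can say so. If the count in item 3 is zero, the main and supportive tables coincide.

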3.5 Patient Experience Data (PED)

PED will be collected for Study 1 and Study 2 at each subject's Baseline Visit only.

3.6 Safety Endpoints

Study 1 and Study 2 will be analyzed and reported independently for safety. The following safety evaluations will be performed during Study 1 and Study 2: treatment-emergent adverse events (TEAEs), serious adverse events (SAEs), AE of special interest (AESI), AEs leading to discontinuation, vital signs, laboratory tests, and physical examination findings.

3.7 Pharmacokinetic Endpoints

Study 1 and Study 2 will be analyzed and reported independently for pharmacokinetic (PK) endpoints. PK samples will be collected from approximately 30% of subjects at select sites at the visits indicated in [Appendix D](#). Using the data available from these subjects, a nonlinear mixed-effects modeling approach will be used to estimate the population central values and the empirical Bayesian estimates of the individual values of upadacitinib oral clearance (CL/F) and apparent volume of distribution (V/F). Additional parameters may be estimated if useful in the interpretation of the data. Data from these studies may be combined with data from other studies for the population PK analyses.

3.8 Biomarker Research

Optional samples for biomarker research will be collected in Study 1 and Study 2 as described in [Appendix D](#) to evaluate known and/or novel disease-related or drug-related biomarkers. Types of biomarkers may include nucleic acids, proteins, lipids, and/or metabolites. The objective of the research is to analyze samples for biomarkers that will help to understand axSpA, related conditions, and response to treatment with upadacitinib or similar compounds. Research may also include changes in epigenetics, gene expression, and proteomics that may associate with axSpA, related conditions, or the subject's response to treatment. This research is exploratory in nature, and the results may not be included with clinical study reports.

